7.2.1 Anticipated Adverse Events and Adverse Device Effects

The following complications have been reported for other commercially available Cardiac Mapping Systems (and competitive systems) and are expected to be similar to those anticipated in this registry. Possible anticipated adverse events are including, but not limited to:

- Map shifts without warning or error message
- Complete signal loss of one or more channels
- Pacing malfunction
- Incorrect catheter display
- System freeze/Slow processing
- Electrical shock
- Signal interference
- System shutdown
- Signals duplicated on two separate channels
- Perforation
- Significant signal noise
- Miscellaneous error requiring procedure cancellation
- Loss of data display
- Pacing routed through wrong channel
- Unwanted pacing initiated by the system
- Metal interface
- Bent pins on output cable
- Allergic reaction – Patches
- Temperature too low for ablation
- PIU overheating

The following complications have been reported for commercially available catheters or in published literature and are expected to be similar to those anticipated in this registry. Possible anticipated adverse events are any events associated with any EP procedure including, but not limited to:

- Transient Ischemic Attack (TIA)
- Coronary Sinus dissection or perforation
- Valve damage
- Thrombotic or air embolism
- Hemothorax
- Pericardial effusion
- Unintended complete or incomplete AV, SN or other heart block
- Venous thrombosis
- Endocarditis
- Local tissue reaction
- Death (is result of AE)
- Possible allergic reaction to conscious anesthetic sedation medication or short term exposure to heparin
- Cardiac damage
- Tamponade
- Induced atrial or ventricular arrhythmias
- Pneumothorax
- Myocardial irritability/infarction
- Pleural effusion
- CHF exacerbation or pulmonary edema
- Excessive bleeding
- Infection
- Formation of fibrotic tissue
- Hematoma/seroma
- Vascular perforation or dissection
- Catheter entrapment within the heart or blood vessels
- Atrio-esophageal fistula

These AEs are not unique to catheters being used within the registry and could occur as a result of any EP procedure outside of the registry.

Anticipated non cardiac events are, but not limited to:

- Air embolism
- Cerebral Vascular Accident (CVA)
- Laceration
- Pneumonia
- Pulmonary hypertension
- Respiratory depression
- Anesthesia reaction
- High creatinine phosphokinase
- Phrenic nerve damage
- Pulmonary embolism
- Pseudo-aneurysm
- Sepsis

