12.0 STATISTICAL CONSIDERATIONS

12.1 Statistical Design, Hypotheses, Method and Analytical Procedures

This is a multi-center, observational, prospective registry. The objective of the registry is to assess and characterize the use and performance of the EnSite Precision™ Cardiac Mapping System and EnSite Precision™ Software v2.0 (The System) in a variety of electrophysiological (EP) procedures and clinical settings.

The endpoints for characterizing and evaluating the objective are as following:

Primary Endpoints:

- EnSite Precision™ Software v2.0 Assessment
 - Accuracy of geometry: Proportion of subjects with accurate geometry
 - Overall system stability: Proportion of subjects with overall system stability
 - Unrecoverable shifts: Proportion of subjects whose map could not be recovered

- Automap™ Module Assessment
 - Mapping time associated with (re-)mapping one or multiple arrhythmias in a single subject with a variety of catheters; mapping time will be summarized (using mean, median, standard deviation, minimum and maximum across arrhythmia types, and for each type of arrhythmia as appropriate) for the following modules:
 - Manual
 - AutoMap™
 - TurboMap™
 - Point density associated with (re-)mapping one or multiple arrhythmias in a single subject with a variety of catheters; mapping points collected and used will be summarized (using mean, median, standard deviation, minimum and maximum across arrhythmia types, and for each type of arrhythmia as appropriate)

Secondary Endpoints:

- EnSite Precision™ Cardiac Mapping System Assessment
 - Ease of Use: Proportion of subjects in whom the mapping system was reported to be excellent, very good, good, poor and N/A
 - Overall Procedure time: will be summarized using mean, median, standard deviation, minimum and maximum

- AutoMark feature Assessment
 - Clinical Utility of the automated RF marker placement: proportion of subjects where the AutoMark feature assisted in identifying gaps in lesion lines
 - Ease of Use of the automated RF marker placement: proportion of subjects where the AutoMark feature was easy to use

Analysis method:

The analysis population will include subjects who have signed the Informed Consent Form and undergone the CIP defined EP study and ablation procedure. Endpoints will be summarized based on available data or measurements in the analysis population, as appropriate.

Clinical Investigational Plan

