Data will be categorized and summarized using appropriate descriptive statistics. Continuous data will be summarized using descriptive statistics such as the number of non-missing data, mean, standard deviation and/or median, minimum, or maximum. Categorical data will be summarized using frequency count and its percentage.

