12.9 The Treatment of missing, unused or spurious Data, including Drop-outs and Withdrawals

All data available for the endpoints specified among the analysis population will be used as appropriate. No imputation will be used treat missing data.

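### The plan has no scoring rule for cases abandoned or cancelled because of a system fault, so they can drop out of the primary Software V2.0 proportions in the system's favour

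*Combined protocol and SAP*

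**What the plan says.** Section 12.1 defines the three primary Software V2.0 endpoints as proportions of subjects: "Accuracy of geometry: Proportion of subjects with accurate geometry"; "Overall system stability: Proportion of subjects with overall system stability"; and "Unrecoverable shifts: Proportion of subjects whose map could not be recovered". No denominator is given beyond the analysis population.

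That population is set in the same section and repeated in 12.8: "The analysis population will include subjects who have signed the Informed Consent Form and undergone the CIP defined EP study and ablation procedure". Within it, "Endpoints will be summarized based on available data or measurements in the analysis population, as appropriate". Section 12.9 adds: "No imputation will be used treat missing data".

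On reporting, "Continuous data will be summarized using descriptive statistics such as the number of non-missing data". For categorical data, which include the three proportions, the plan offers a count and a percentage and does not mention the number assessed.

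Section 7.2.1 lists anticipated events for mapping systems. They include system freeze, system shutdown, loss of data display and "Miscellaneous error requiring procedure cancellation". No section says how a subject with such an event is scored on the primary proportions.

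**The concern.** If a subject is unassessed because the system failed, the data are missing for the very reason the endpoint exists to measure. There are two routes by which such a subject can be lost.

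- **Treated, system given up.** The ablation is completed, so the subject belongs to the analysis population, but the geometry or stability field may be blank. The available-data rule then removes the subject from the denominator.
- **Cancelled before ablation.** The subject never enters the analysis population, so no missing-data rule, however worded, would bring the case back.

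The registry tests no hypothesis, so these proportions are its main output on software performance. Section 17.0 commits to publication, and section 9.0 allows the data to be used in support of a market-approval application. The number unassessed need not be reported for a categorical endpoint, so a reader of the final report might be unable to tell whether any failures had been left out.

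**Working it through.** **Inputs from the plan.** Available-data rule (12.1), no imputation (12.9), analysis population (12.1, 12.8), anticipated system faults (7.2.1), enrolment of up to 500 (12.2).

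**Inputs assumed.** The documents give neither of these:
- p, the accurate proportion among assessed subjects, taken as 0.90 to 0.98;
- a, the fraction of subjects with mapping attempted who drop out by either route because of a system fault, taken as 1% to 5%.

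**Step 1: the plan's own figure.** Section 12.2 wants 50 subjects per arrhythmia type at a lowest expected rate of 10%: 50 / 0.10 = 500. This reproduces and is not affected by the point. It is used below only for scale.

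**Step 2: formula.** Of N attempted cases, aN drop out and (1 − a)N are assessed, of whom p(1 − a)N are accurate. The plan reports p. Counting the drop-outs as failures gives p(1 − a). The overstatement is p − p(1 − a) = p × a, which cannot be negative.

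**Step 3: numbers.** Each cell shows the failure-counted proportion, with the overstatement in percentage points in brackets.

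| a | Cases of 500 | p = 0.90 | p = 0.95 | p = 0.98 |
|---|---|---|---|---|
| 1% | 5 | 89.1% (0.90) | 94.05% (0.95) | 97.02% (0.98) |
| 2% | 10 | 88.2% (1.80) | 93.1% (1.90) | 96.04% (1.96) |
| 5% | 25 | 85.5% (4.50) | 90.25% (4.75) | 93.1% (4.90) |

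**Step 4: if some faults are already scored.** Suppose 5% of subjects have such a fault, half of them are recorded as inaccurate anyway, and 95% of the rest are accurate. The available-data figure is 0.95 × 0.95 / 0.975 = 92.6%, against 90.25% with all faults counted, so the gap is 2.3 points. If all are recorded as inaccurate, nobody drops out (a = 0) and the gap is zero.

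**Step 5: map recovery.** If u is the assessed proportion with an unrecovered map and every drop-out lost its map, the failure-counted figure is u + a(1 − u). With u assumed at 1%, this is 1.99% at a = 1% and 5.95% at a = 5%. It is an upper bound, since a case can be abandoned without losing the map.

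**Step 6: why the size is given in points and not as a ratio.** The ratio of failure rates depends on how many assessed geometries are inaccurate, which is also unknown.
- 5 inaccurate, 10 dropped: 5/490 = 1.0% against 15/500 = 3.0%, ratio 2.9.
- 25 inaccurate, 10 dropped: 25/490 = 5.1% against 35/500 = 7.0%, ratio 1.4.
- 25 inaccurate, 5 dropped: 25/495 = 5.1% against 30/500 = 6.0%, ratio 1.2.

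**The case against.** The strongest reply is that nothing in the documents says these subjects go unassessed. Accurate geometry has no stated criterion, assessor or time point, and the eCRFs and procedure guidelines are held separately (Appendices D and G). A form that records an inaccurate geometry when the system fails would supply available data and leave no bias. A geometry may also be completed and judged before a later shutdown, and section 5.5 has the whole study backed up and returned to the sponsor. This stands. A reader might infer that abandoned cases necessarily have no geometry, but the documents support only that they may have none.

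A second reply is that failures show up elsewhere. Stability and map recovery are primary endpoints too and may register some of them. Section 7.2 requires all adverse device effects and product complaints to be reported, and the synopsis says performance is assessed partly from adverse events. So the failures are not invisible. But stability and map recovery follow the same available-data rule, and no section 12.1 endpoint draws on event or complaint reports. Registering a failure elsewhere does not restore it to the geometry denominator.

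Third, the registry is descriptive, with no pass/fail criteria (12.3) and no hypothesis test (12.10). That limits the consequence but does not make an ambiguous proportion clear.

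On mapping time, a reader might infer that AutoMap times are cut short when a map is finished manually. The documents do not describe such switching, so that remains a possibility only. Charging the whole time to the starting module would not be a remedy, because it would put manual time into an AutoMap figure that 12.1 summarises by module.

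**Conclusion.** The point holds as a gap in the plan with a one-sided risk. Sections 12.1, 12.8 and 12.9 state neither the scoring nor the denominator for cases abandoned, replaced or cancelled because of a system fault, although 7.2.1 foresees faults that could lead to them. If a system fault is regarded as a failure of the system, both routes can only move accurate geometry in its favour, and possibly stability and map recovery as well.

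The overstatement of accurate geometry is p × a: zero if every such case is already scored as a failure, and about 1 to 5 percentage points if 1% to 5% of cases drop out and none is scored. Neither a nor p is in the documents. They therefore do not support saying that performance is overstated by a known amount, or that failure is understated two- to threefold. A ratio of that size needs very few inaccurate geometries among those assessed. The sample size is unaffected. The change should be made, but the registry's descriptive purpose does not depend on it.

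**What to change.** Amend 12.1, 12.8 and 12.9 for the Software V2.0 primary proportions as follows.

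- **Denominator:** all consented subjects in whom mapping with the EnSite Precision system was attempted, including procedures cancelled for a system error.
- **Scoring:** a case abandoned, replaced or cancelled because of a system fault counts as a failure for geometry and for stability. If a geometry was completed and judged before the fault, that geometry judgement stands. Where the map was lost, the case also counts as a failure for map recovery.
- **Limit:** switches made at the physician's discretion for reasons unrelated to the system do not count as failures. The synopsis and section 4.1 already allow discretionary use of other tools.
- **Reporting:** give the available-data proportion as a second figure, with the number assessed, the number missing and the reasons.
- **Mapping time:** report how many maps were switched between modules and summarise those maps separately.

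The cost is a wording change, one or two procedure eCRF fields (system given up or module switched, with the reason), and slightly less favourable reported figures.

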3.2.1 Number of subjects required to be included in the registry

Up to 500 subjects will be enrolled in up to 50 sites worldwide. No site can enroll more than 15% (i.e. 75 patients) of the sample size.

Each site is allowed to enroll subjects with any arrhythmia qualified for ablation.

NOTE: A variety of arrhythmias (atrial and ventricular in origin) is strongly recommended.

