12.2 Sample Size

It is estimated that ventricular tachycardias would occur at a rate of 10%. The study will characterize mapping time and point density for a minimum of 50 subjects with each type of arrhythmia. Since Ventricular Tachycardia is expected to occur at the lowest rate (10%), up to 500 subjects will be enrolled in this registry.

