12.10 The Exclusion or particular Information for the testing of the hypothesis

Not applicable as hypothesis testing will not be performed.

12.11 The minimum and maximum Number of Subjects to be included for each Center

It is expected to enroll up to 500 subjects in up to 50 centers worldwide. The maximum number of subjects to be included at each enrolling center is 75 (15% of total enrollment) subjects, in an effort to have a balance of the subjects across participating centers. The minimum number of subjects to be included at enrolling centers is 1.

Clinical Investigational Plan

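### The three primary software proportions are to be reported as count and percentage with no confidence interval, so zero unrecoverable shifts in 500 would appear as 0% when the exact 95% upper limit is 0.74%

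*Combined protocol and SAP*

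**What the plan says.** Section 12.1 defines the three software endpoints as single-arm proportions: "Accuracy of geometry: Proportion of subjects with accurate geometry"; "Overall system stability: Proportion of subjects with overall system stability"; and "Unrecoverable shifts: Proportion of subjects whose map could not be recovered".

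The analysis method at the end of that section is general: "Data will be categorized and summarized using appropriate descriptive statistics". For categorical data it is specific: "Categorical data will be summarized using frequency count and its percentage". For continuous data the same paragraph lists the number of non-missing values and the standard deviation among the summaries. It lists no counterpart for proportions.

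The rest of section 12 adds no measure of precision. Section 12.3 says pass/fail criteria do not apply, and section 12.10 says there will be no hypothesis testing. Section 12.9 uses available data without imputation. Section 12.2 sets the sample size from the number of ventricular tachycardia (VT) subjects wanted, not from the width of any interval.

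Site enters in two places. Section 12.11 sets a cap: "The maximum number of subjects to be included at each enrolling center is 75 (15% of total enrollment) subjects". Section 12.7 allows optional summaries by center.

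**The concern.** The registry is meant to characterize performance (section 3.3.1), and its data are to be used to evaluate clinical performance (section 3.1). Section 17.0 commits to submitting the results for publication, and section 9.0 foresees possible use in support of a market-approval application. Readers will therefore apply these percentages beyond the subjects enrolled. With no test planned, the estimate and its uncertainty are all the registry can offer on the three software endpoints, and the plan provides only the estimate.

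The gap shows most clearly for unrecoverable shifts. If none were seen, the planned summary would be a count of zero and 0%, with nothing to show which true rates remain compatible with that result.

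Clustering is a second, smaller matter. Procedures follow each center's standard practice and sensor-enabled catheters are optional (section 5.5), so some similarity of outcomes within a site is plausible. An interval that treats all subjects as independent could then be too narrow.

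**Working it through.** **Inputs from the documents.** Maximum of 500 subjects and 50 sites (section 3.2.1); site cap 75 (section 12.11); VT rate 10% and at least 50 subjects per arrhythmia type (section 12.2). The documents give no expected rate for any of the three proportions and no ICC. ICC values of 0.01, 0.05 and 0.10 are assumed below.

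**The plan's own figures.** 50 / 0.10 = 500 and 0.15 × 500 = 75, so both reproduce. There is no alpha, power or precision formula to check. If both maxima are reached, the average is 500 / 50 = 10 subjects per site.

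**Zero events, independent subjects.** The exact (Clopper-Pearson) two-sided 95% upper limit for 0 out of n is 1 − 0.025^(1/n).

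- n = 500: 1 − 0.025^(1/500) = 0.74%, about 1 in 136.
- n = 400, if the evaluable number falls short of the maximum: 0.92%.

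Put the other way, the chance of seeing no event in 500 is (1 − p)^500. A true rate of 0.5% gives 0.995^500 = 8.2%, and a true rate of 0.2% gives 0.998^500 = 36.8%.

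**More common outcomes, independent subjects (illustrative).** Exact 95% limits are 87.0% to 92.5% for 450/500 (90%), and 92.7% to 96.7% for 475/500 (95%).

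**Site clustering.** Design effect = 1 + (m − 1) × ICC; effective n = 500 / design effect; the exact limits are then computed at the effective n. With m = 10:

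| Assumed ICC | Design effect | Effective n | Upper limit, 0 events | Interval at 90% | Interval at 95% |
|---|---|---|---|---|---|
| 0.01 | 1.09 | 458.7 | 0.80% | 86.9–92.6% | 92.6–96.8% |
| 0.05 | 1.45 | 344.8 | 1.06% | 86.3–93.0% | 92.1–97.0% |
| 0.10 | 1.90 | 263.2 | 1.39% | 85.7–93.3% | 91.6–97.3% |

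These figures assume equal site sizes. Unequal recruitment raises the design effect, because the relevant m is then the size-weighted mean, Σm² / Σm.

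**Which clustered methods work with zero events.** A bootstrap that resamples sites draws only zeros and returns 0% to 0%. A cluster-robust variance is also zero. The ICC cannot be estimated from data without events. Only an assumed range of ICCs gives a usable clustered limit.

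**The case against.** The strongest reply is that this is a descriptive registry. No decision rule depends on an interval, and the general wording of section 12.1 does not forbid one. Counts accompany the percentages, so a reader who has the denominator can derive a simple exact interval. At the full sample size the unclustered gap is small: 0% against 0.74%. All of this stands, and it limits the weight of the point. It does not remove it: the interval is not prespecified, the non-missing denominator is not promised for categorical data, and no reader could work out a clustered interval from the overall count.

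A reader might infer several stronger claims that the documents do not support.

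- **That 0 out of 50 VT subjects and 0 out of 500 would both be shown as 0%.** The plan does not commit to showing the three proportions by arrhythmia type. Section 12.1 attaches by-type summaries to mapping time and point density only. The minimum of 50 serves those same endpoints: "The study will characterize mapping time and point density for a minimum of 50 subjects with each type of arrhythmia". Section 12.7 prespecifies no subgroup analysis.
- **That shifts are expected to be near 0%.** Section 7.2.1 lists map shifts among anticipated events but gives no frequency. The zero-event case is an illustration.
- **That every site might reach 75.** This would mean about 500 / 75 = 6.7 sites, against a plan of up to 50. The resulting upper limits for 0/500 (1.28% to 6.01% over the same ICC range) are an extreme bound, and section 12.11 says the cap is there to balance enrollment across centers.
- **That subject-level intervals should extend to every secondary proportion.** The User Experience Form is completed once per physician (section 5.5). If ease of use is taken from that form, the subject would be the wrong unit, and the case report forms are not available to settle this.

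**Conclusion.** The point holds for the three overall primary proportions. Section 12 plans to report them without any measure of precision, in a registry whose only output is estimation. In the illustrative zero-event case at the full 500, 0% would be reported with an exact 95% upper limit of 0.74%. At an average of 10 subjects per site and an assumed ICC of 0.01 to 0.10, that limit is 0.80% to 1.39%. For proportions of 90% to 95%, the unclustered interval extends roughly 2 to 3 percentage points either side.

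The event counts and ICC range are assumptions, not figures from the plan. The clustered limits also assume that both enrollment maxima are reached with sites of equal size. The percentages themselves would not be wrong and no test is invalidated; what is missing is a statement of how firmly the data support them.

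**What to change.** Amend the analysis method in section 12.1 as follows.

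1. Report each overall primary proportion with its non-missing denominator and an exact (Clopper-Pearson) two-sided 95% confidence interval. For any zero-event result, state the upper limit beside the 0%.
2. Add a sensitivity interval for site clustering: exact limits at a design-effect-adjusted n, over an ICC range stated in advance (for example 0.01 to 0.10), using the site sizes actually achieved. Do not use a cluster bootstrap or robust variance when there are no events.
3. Do not add breakdowns by arrhythmia type that the plan does not contain. If the proportions are shown by type, attach the same exact interval.

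The cost is a few sentences in section 12.1, agreement on the ICC range, and minor extra programming. No subject, visit or data item is added. Fixing the method now also prevents the interval from being chosen after the results are known.
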